## BACKGROUND

It is known that the vagus nerve is one of the main determinants of gastrointestinal motility and gastric emptying. For example, truncal vagotomy produces gastroparesis in both animals as well as human subjects. It is speculated but never proven that neuropathy of the vagus nerve is the cause of the delay in gastric emptying that is characteristic of that disorder.

The typical symptoms of gastroparesis are nausea, vomiting, weight loss, early satiety, abdominal pain and bloating. The initial medical treatment consists of dietary alterations and medications such as phenothiazines (Phenergan), 5HT3 receptor agonists (Zofran) and cannabinoids (Marinol). Treatment with prokinetic agents such as metoclopramide, domperidone, erythromycin and cisapride can be considered but the prolonged use of these agents is limited by the frequent neurologic and cardiac side-effects of these agents. In severe cases patients require placement of a gastrojejunostomy feeding tube (GJ) tube which bypasses the gastroparetic stomach or even intravenous feeding such as total parenteral nutrition (TPN) in which the patient's entire nutrition is dependent on intravenous fluids.

Gastric electrical stimulation (GES) has been shown to be an effective treatment of nausea and vomiting in patients with gastroparesis (1). However, how GES works is unclear, as patients who undergo GES show resolution of nausea and vomiting before any improvement in gastric emptying is recognized. It has been proposed, but never proven, that GES may influence vagal outflow via afferent fibers that terminate in the CNS.

The vagus nerve is composed of both myelinated and unmyelinated fibers and one of the specific unknown factors is precisely which elements of the nerve are activated by stimulation with various output settings of the stimulator. Stimulation of a peripheral or cranial nerve with a mixed fiber population generates a compound nerve action potential (CNAP) composed of various nerve fibers which conduct the electrical impulse at various rates.

Our current investigations show that it is possible to measure vagus nerve CNAPs during gastric electrical stimulation with cutaneous ECG electrodes placed on the neck. Our studies show that gastroparetic patients who exhibit high-amplitude CNAPs show significant improvement in symptoms such as nausea, vomiting and early satiety than patients who demonstrate lower amplitude vagal nerve CNAPs. The PI currently has an active IRB protocol designed to further evaluate the effect of vagal nerve CNAPs on symptom control in gastroparetic patients (IRB# 1206008988). Another study that is currently undergoing is the effect of the ABVN stimulation on the vagal nerve CNAPs (IRB number 1809683671). These investigations indicate that generation of vagus nerve CNAPs appear to be factorial in symptom control in gastroparetic patients. The study in healthy volunteer is still under data analysis, but the preliminary results do look promising.

Despite its efficacy in some patients, gastric electrical stimulation of the stomach has its drawbacks. These are 1) its expense; 2) it is an invasive procedure and requires surgical implantation of a foreign body into the patient's abdomen; 3) it is not universally effective and it is difficult to predict with any precision which patient will respond to treatment and which will not; 4) the device battery life is finite and patients typically require another surgical procedure to replace the battery within five to ten years; 5) as the device is metallic, patients are unable to undergo MRI scans for any other medical conditions. Given these considerations another less invasive modality to electronically stimulate the vagus nerve would be highly desirable.

Recent investigations have demonstrated the feasibility of physiological access to the vagus nerve through its auricular branch; namely, the auricular branch of the vagus nerve (ABVN) which in human subjects is located near the external auditory meatus. Both the nucleus tractus solitarius (NTS) and the spinal trigeminal nucleus receive somatosensory afferents through the auricular branch (2-4) and neuroimaging studies show that transcutaneous stimulation of the ABVN modulates brainstem and cortical areas in a manner similar to classical vagal nerve stimulation (5-7). A recent clinical trial suggested that auricular branch vagal nerve stimulation (ABVN) also reduces the frequency of migraine episodes (2), while another independent investigation demonstrated that stimulation of the ABVN influences respiratory variation of heart rate in human subjects (8). This finding supports the notion that this technique can be useful in modulating parasympathetic outflow of the vagus nerve.

## COLLABORATIVE ARRANGEMENTS

The current proposal is generated at the behest of [name] of the NIH Office of Strategic Coordination. Both the PI [name] and [name] (Indiana University and Purdue University, respectively) have active funding from the NIH SPARC program (Stimulating Peripheral Activity to Relieve Conditions) to evaluate vagally mediated compound nerve action potentials in gastroparetic patients. The other coinvestigators named in this proposal, Drs [name], [name] and [name], all from Harvard University, likewise have active research support from the NIH. Their research involves electrical stimulation of the auricular branch of the vagus nerve as described in the paragraphs above. As one of the goals of the SPARC program is to promote collaborative research among institutions [name] suggested that Indiana, Purdue and Harvard University combine their efforts to evaluate the effects of noninvasive ABVN stimulation on vagal nerve function.

Both the PI and Co-PI (Drs [name] and [name]) travelled to Boston in July 2018 to meet with the Harvard investigators and to formulate a study plan and a cooperative effort. The technique of ABVN stimulation as described above is adapted from the protocol in

place at Harvard University. A letter of collaborative support from [name] is included with this application (Appendix 2).

## **STUDY OBJECTIVES**

The research described in this protocol is an extension of our current protocols which is designed to measure cervical compound vagal nerve action potentials in patients who have an implanted gastric electrical stimulation device (IRB# 1206008988) and also the protocol to measure the effect of ABVN stimulation and vagal maneuvers in healthy volunteers. Healthy volunteer subjects and gastroparetic subjects will be recruited and studied for this project, volunteer subjects will undergo transcutaneous stimulation of the auricular branch of the vagus nerve (ABVN) to determine whether this modality will also produce cervical vagus nerve compound action potentials and changes in the gastric hormones. Gastroparetic subjects who have not had a gastric stimulator placed will also undergo the ABVN stimulation to look for changes in vagal nerve CNAPs and gastric hormones.

Additionally, as there are currently no physiological methods that can record and measure gastric vagal activity in human subjects, a separate component of this study will be to measure the gastric vagal activity in humans. If the proposed study shows that it is indeed possible to record a vagal “signature” in response to electrical stimulation, then we anticipate further investigations which examine the vagal response to other gastric stimuli.

Due to the low signal-to-noise ratios observed from compound vagal nerve activity in response to GES, we are interested in measuring the vagal response to maneuvers which are known to stimulate the vagus nerve. The implementation of these vagal maneuvers will allow comparison of ABVN stimulation to traditional methods of vagal stimulation.

Based on our healthy volunteer study and our proposal with NIH, we would like to propose some additional features. We would like to study the effect of transcutaneous stimulation of the auricular branch of the vagus nerve (ABVN) in gastroparetic patients with symptomatic nausea and vomiting who have not undergone gastric electrical stimulation device implantation.

A total of 40 gastroparetic patients will be enrolled with 20 diabetic and 20 idiopathic patients.

Also, we propose to study the effect on gastric hormone before, during and after auricular stimulation.

The proposal is to enroll 30 healthy volunteers with no gastric symptoms to undergo transcutaneous stimulation of the auricular branch of the vagus nerve and also undergo

**PI: [name] Effect of Electrical Stimulation of the Auricular Branch of the Vagus Nerve on Cervical Vagus Nerve Compound Action Potentials**

blood draw before, after stimulation and later a third draw after a period of no stimulation.

This is based upon the results obtained in our previous IRB approved study where blood was drawn in patients who had gastric electrical stimulation device implanted. Blood was drawn to study the effects of stimulation on gastric hormones. (Cardiac Vagal Effects of Gastric Electrical Stimulation and Vagal Nerve Action Potentials in Vagus nerve in Patients with Gastroparesis- IRB 1206008988)

The next part is also to enroll 40 gastroparetic subjects to undergo blood draw before, after transcutaneous stimulation of the auricular branch of the vagus nerve, and a third draw after a period of no stimulation. Another part is to enroll 40 gastroparetic subjects to undergo vagal maneuver that includes food study using the bipolar (EKG electrodes).

Another part is to enroll 10 healthy volunteers to undergo vagal maneuver using the Multi Array Electrodes (MEA)

An additional 15 subjects who have no GI symptoms (otherwise healthy) but have undergone Vagal Nerve Stimulation (VNS) Therapy for the treatment of partial or focal seizures will be recruited for the study.

## **INVESTIGATIONAL PLAN**

Healthy human subjects ranging in age between 18 to 80 years and who are able to give informed consent are considered candidates for study. Pregnant subjects are excluded from study.

The consent may be administered by the study team either in person or virtually using RedCap platform.

A modality of therapy currently being utilized to treat focal or partial seizures that do not respond to seizure medications is called as VNS Therapy (Vagus Nerve Stimulation). This has been approved by FDA as an effective treatment for seizure disorders. Our aim is to study the HRV in patients undergoing this therapy as part of their regular mode of treatment. The specific aim is to measure the HRV in patients undergoing vagus nerve stimulation therapy.

[figure not shown]
During VNS treatment the stimulator is surgically implanted in the upper chest and stimulation electrodes are implanted in the left cervical vagus nerve.

### **Technique of transcutaneous auricular vagus nerve stimulation**

Two electrodes are placed in the auricle of the left ear at loci described by the (1) the cyma concha and (2) the slope between the antihelix and cavum concha (Figs. A and B).

These locations are chosen based on auricular sub regions with the greatest probability of vagal innervation of the human auricle, as has been previously determined by cadaver dissection (9) Electrodes are passed through the penetration panel with inline low-pass radio frequency filtering (80 MHz). Electrical stimulation to these electrodes is provided by a constant-current stimulator with 100 V compliance (FE 180 Stimulus Isolator, AD Instruments, Boston MA).

Stimuli consist of rectangular pulses with 450  $\mu$ s pulse width, delivered at 30 Hz, and pulse train duration of 0.5 seconds, as previously described in studies of chronic pain patients (10). Stimulation is gated, with 0.5-second delay, after peak inhalation (i.e., during exhalation) or after peak exhalation (i.e., during inhalation).

Respiratory gating for stimulation requires real-time evaluation of the respiratory cycle. We use a respiratory belt transducer designed to measure changes in chest diameter resulting from breathing (Fig. C). This pneumatic belt is placed around the subject's lower thorax at the level of maximum respiratory expansion (TN 1132/ST Respiratory Belt, AD Instruments, Boston MA). The belt is pretensioned slightly. The belt contains a capacitive sensing element and custom electronics that respond linearly to changes in length. The transducer is connected to a PowerLab pod port (Power Lab, AD Instruments, Boston MA). The transducer contains a flexible sensing element bonded to the inside of the fabric belt.

Once electrode placement in the ear is validated, subjects are asked to rate stimulation intensity of 0 to 10 (0: no sensation, 10: mild discomfort). Current intensity is set to achieve moderate to strong (but not painful) sensation (target score: 4/10), and this current intensity is used on subsequent stimulation runs. For SHAM baseline study, the electrode in the ear remains in place, but the leads are disconnected from the stimulator.

### **Measurement of cervical vagal nerve compound actions potentials and electrogastrogram (EGG)**

The Principal Investigator has an active IRB protocol which examines cutaneous cervical vagal nerve compound nerve action potentials (CNAPS) and the cutaneous electrogastrogram (EGG) in patients with gastroparesis who have undergone implantation of a gastric electrical stimulation device. We refer to IRB protocol “Cardiac Vagal Effects of Gastric Electrical Stimulation and Vagal Nerve Action Potentials in Vagus nerve in Patients with Gastroparesis” (IRB# 1206008988). . Briefly ECG electrodes are

placed on the chest and arms or legs of each subject as well as on the neck overlying the right and left vagus nerves. To measure the cutaneous electrogastrogram (EGG) a set of three ECG electrodes are placed over the upper abdomen in a line parallel to the longitudinal axis of the stomach. Again, we refer to the protocol itself for further details.

#### ABVN Phase 2 Outcome Measures/Endpoints

1. To measure the amplitude of vagal nerve compound action potentials in gastroparetic subjects with symptoms of nausea and vomiting with skin electrodes over right and left vagus nerve during ABVN stimulation and also during the vagal maneuvers phase
2. To measure respiratory changes in heart rate during ABVN and also during the vagal maneuvers phase.
3. To measure changes in the amplitude of the surface electrogastrogram during ABVN and also during the vagal maneuvers phase.
4. To measure the Heart rate variability(HRV), vagal nerve compound action potentials and electrogastrogram in subjects undergoing VNS Therapy for focal or partial seizures.
5. To measure the effect of ABVN stimulation on the gastric hormones in healthy and gastroparetic subjects.
6. To see the effect on the data if we change the regular ECG electrodes to MEA electrodes in the neck.
7. To see the effect of COVID 19 on HRV in healthy volunteers diagnosed with COVID-19

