#### **EAR STIMULATION GROUP:**

This is a onetime visit only that involves baseline and test procedures.

1. Two MRI compatible electrodes will be placed in the auricle of the left ear, fixed by a plastic armature that wraps around the ear. The leads from the electrodes are connected to a stimulator.
2. A pneumatic belt may be placed around the lower thorax. Pneumatic tubes connect this belt to a pressure transducer that in turn sends signal to a laptop-controlled device that acquires the signals.

3. Two ECG electrodes are placed on both sides of the neck overlying the area near the carotid artery where the vagus nerve is superficial. This is to measure the vagal action potentials in the neck.
4. Two ECG electrodes are placed one on each arm and one on the chest for measurement of the electrocardiogram (ECG)
5. Three ECG electrodes are placed on the abdomen in a line parallel to the longitudinal axis of the stomach to record the electrogastrogram (EGG).

Electrical stimulation of the electrodes placed in the ear is provided by a current-constant stimulator. The stimuli consist of rectangular pulses with  $450\text{ }\mu\text{s}$  pulse width, delivered at 30 Hz, and pulse train duration of 0.5 seconds. Stimulation is gated, with 0.5-second delay, after peak inhalation (i.e., during exhalation) or after peak exhalation (i.e., during inhalation).

Baseline procedure:

A butterfly catheter is inserted under aseptic conditions into a peripheral vein. Fifteen ml (1 tablespoon) of blood is withdrawn and placed on ice. After this the baseline recording will be started as described below.

During the baseline recording the stimulating electrodes are placed in the auricle of the subject but no current is delivered. Cervical neck electrodes are placed over the right and left vagus nerve to record any electrical activity that might occur during the baseline period. Baseline ECG and EGG recordings are also performed during this interval.

Test procedure:

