Stimuli consisting of rectangular pulses with  $450\text{ }\mu\text{s}$  pulse width, delivered at 30 Hz, and pulse train duration of 0.5 seconds are then delivered to the subject. Current intensity is set to achieve moderate to strong (but not painful) sensation, and pulse frequency/duration is set following pilot testing to achieve a subjectively comfortable stimulus sensation. Starting current is 0.1mA and the maximum current that can be given will not exceed 5.0 mA. This is 4 out of 10 and is designated “100 per cent.” The current amplitude is then increased again by 10 per cent and ABVN is applied again for 60 seconds. This sequence is repeated until the “100 percent” level (4/10) is reached. Based on the previous study we find that the target of 4/10 may correlate with a current of somewhere between 1.0 and 3.5 mA, but this is variable from subject to subject.

Sensation of 10/10 may correlate with close to 10.0 mA. The time that may elapse from the start to reaching the 100% target is very variable and may range from 5 minutes to 15 minutes. It depends upon how soon the subject reaches the subjective 4/10 sensation. These stimuli are delivered during expiratory phase of respiration as investigations have shown this to be most effective in producing vagal stimulation (8).

Once the target stimulus intensity has been achieved, stimuli are delivered during the expiratory phase for a total of two minutes. Another 15 ml (1 tablespoon) of blood will be collected 20 minutes after stopping the stimulus.

The subject will be allowed to keep on resting and 20 minutes after the second blood draw, another 15 ml (1 tablespoon) of blood will be drawn. This is the final draw. The catheter will then be withdrawn, and the subject will be allowed to go home

ECG and EGG recordings are continued during auricular branch vagal nerve stimulation.

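### The no-sensation baseline cannot separate a vagal effect on endpoint 2 from a change in breathing during ABVN, and the protocol does not secure the breathing record needed to check

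*Protocol*

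**What the plan says.** **Endpoint.** Item 2 of the protocol's ABVN Phase 2 Outcome Measures/Endpoints is "To measure respiratory changes in heart rate during ABVN and also during the vagal maneuvers phase". No metric, contrast or model is attached to it.

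**Comparison period.** The section Technique of transcutaneous auricular vagus nerve stimulation states: "For SHAM baseline study, the electrode in the ear remains in place, but the leads are disconnected from the stimulator". Under EAR STIMULATION GROUP, for healthy and for gastroparetic subjects, the baseline recording is made while "the stimulating electrodes are placed in the auricle of the subject but no current is delivered". ECG and EGG are recorded in that interval.

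**Stimulation.** Current is raised to a sensation of 4 out of 10, described as moderate to strong but not painful. On timing, the test procedures say: "These stimuli are delivered during expiratory phase of respiration". The technique section and the set-up text of both ear-stimulation procedures allow gating to exhalation or to inhalation.

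**Breathing signal.** The technique section says that gating needs the respiratory cycle in real time and that this comes from a "respiratory belt transducer designed to measure changes in chest diameter resulting from breathing", which it describes as placed on the subject. Item 2 of the set-up list in both ear-stimulation procedures only says that a belt may be used. If worn, its signal goes to a computer-run acquisition device.

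**Analysis.** Data Analysis compares baseline, which it labels SHAM, with each stimulation level for CNAP amplitude, using ANOVA. It gives no heart-rate analysis. The Background reads an effect of ABVN on respiratory variation of heart rate, seen in another study, as support for modulation of parasympathetic outflow.

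**The concern.** The active and baseline periods differ in two ways: current flows, and the subject feels something tied to each breath. For an outcome unrelated to breathing, the second difference might be tolerable. Endpoint 2 is by name a heart-rate change that goes with respiration, so anything that alters how the subject breathes can alter the outcome directly.

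The attribution is at stake. A change in respiratory heart-rate variation during ABVN would naturally be read in the light of the Background, as evidence of a parasympathetic effect. Without breathing data from both periods, a reader could not judge whether the subject's breathing had simply changed. This has to be settled in the protocol: a later analysis plan can choose covariates, but it cannot recover a signal that was never recorded.

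**Working it through.** The protocol gives no effect size, SD, alpha or power for endpoint 2, so there is no figure to reproduce. The check has two parts.

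**1. The passages side by side**

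| Feature | Baseline (sham) | Stimulation |
|---|---|---|
| Current | none | titrated to 4/10 |
| Sensation | none, since no current | clearly felt |
| Link to the breath | none | triggered after the subject's own respiratory peak |
| ECG | recorded | recorded |
| Belt | placed (technique section); optional (both ear-stimulation procedures) | same conflict, although gating needs it |
| Breathing signal named among the recordings | no | no |

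The contrast therefore mixes current with a breath-locked sensation, and a breathing record is not guaranteed in either column.

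**2. Illustrations (all inputs assumed except the sample sizes)**

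*Size of a breathing-only change.* Assume the heart-rate swing varies as breathing rate to the power −k, with k from 0.5 to 1.5. The ratio of new to old swing is (old rate / new rate)^k.

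- 15 to 12 breaths/min: 1.25^0.5 = 1.12 and 1.25^1.5 = 1.40, a rise of 12% to 40%.
- 18 to 12: 1.5^0.5 = 1.22 and 1.5^1.5 = 1.84, a rise of 22% to 84%.
- No change in rate: ratio 1.00.
- 12 to 15: 0.8^0.5 = 0.89 and 0.8^1.5 = 0.72, a fall of 11% to 28%.

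The sign depends on which way breathing moves, and the documents do not say.

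*Chance of a significant result with zero vagal effect.* Take a paired test at two-sided alpha 0.05 (assumed). If breathing alone shifts the outcome by d SDs of the paired difference, the rejection probability is P(|T| > t(0.975, n−1)), where T is noncentral t with n−1 degrees of freedom and noncentrality d√n. The sizes are 40 gastroparetic subjects, about 30 healthy volunteers, and 20 in each of the diabetic and idiopathic groups.

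| n | d = 0 | d = 0.2 | d = 0.3 | d = 0.5 |
|---|---|---|---|---|
| 20 | 5.0% | 13.6% | 24.7% | 56.5% |
| 30 | 5.0% | 18.5% | 35.5% | 75.4% |
| 40 | 5.0% | 23.5% | 45.7% | 86.9% |

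*Effect of using the breathing record.* Simulation, n = 40, 20,000 runs, zero vagal effect. The breathing difference is B ~ N(shift, 1) and the outcome difference is Y = ρB + √(1−ρ²)·e. Each range runs over ρ = 0.3 and 0.6.

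| Shift in B (SD of B) | Unadjusted | Adjusted for B |
|---|---|---|
| 0 | 5.0% to 5.2% | 4.9% to 5.1% |
| 0.2 | 6.5% to 11.8% | 4.8% to 5.0% |
| 0.5 | 15.3% to 46.3% | 4.8% to 5.3% |
| 0.8 | 31.7% to 84.2% | 4.7% to 5.0% |

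Cross-check: a shift of 0.5 with ρ = 0.6 moves Y by 0.5 × 0.6 = 0.3 SD. The formula gives 45.7% for that shift and the simulation 46.3%.

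**The case against.** The strongest reply is that endpoint 2 has no stated analysis. Data Analysis covers CNAP amplitude only, the statistical analysis plan is not at hand, and a measure called respiratory change in heart rate may itself be computed from the belt trace. This stands. A reader might infer that the breathing signal will be ignored; the documents do not support that, because silence in the protocol does not exclude its use.

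Four further replies also limit the point.

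- The sham comparison is written for CNAP amplitude. For heart rate it is inferred from the ECG taken in the no-current period. The maneuvers have no sham, so only the ABVN half of endpoint 2 is affected.
- The stimulus follows the subject's own breath and imposes no external rhythm. No passage shows that it changes breathing; that it could is an assumption.
- No rule says that a rise in endpoint 2 will be reported as vagal. The Background sentence interprets another study.
- Breathing during stimulation comes after the intervention and may be part of how it acts. An adjusted estimate may remove real effect and cannot serve as the sole test.

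None of these replies supplies what is missing: a baseline that matches the sensation, or a guaranteed breathing record in both periods.

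**Conclusion.** The point holds in limited form. For the ABVN half of endpoint 2, the no-current baseline does not control for breathing changes caused by a felt, breath-locked stimulus. The protocol also contradicts itself on whether the belt that would allow a check is worn.

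The size is unknown. The percentages above rest on assumed exponents, breathing rates, shifts and correlations. A reader might take the 12% to 84% range as an expected upward bias, but it assumes that breathing slows; with no change the bias is nil, and with faster breathing it reverses. The rejection rates show only that, at the planned sizes, a modest breathing shift could matter: 0.3 SD of the paired difference gives a significant result 45.7% of the time at n = 40 against a nominal 5%.

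The change should be made, since it is cheap and cannot be made after the sessions are run.

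**What to change.** 1. Reconcile the technique section with item 2 of both ear-stimulation set-up lists, so that the belt signal is recorded and kept for every baseline (sham) and stimulation window of the ear-stimulation sessions.
2. Report breath interval and chest excursion for each window, so that any change in breathing is visible.
3. Report endpoint 2 unadjusted, with a supportive version adjusted for, or matched on, breath interval and excursion. If the two differ, state that the change may reflect breathing and do not attribute it to vagal outflow alone. Do not make the adjusted result decisive, because breathing may be a mediator.
4. Reconcile the passages that allow gating to either respiratory phase with the test procedures that name the expiratory phase only.

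The cost is small: the belt is already needed for gating, so the additions are fitting it before the baseline recording, storing the trace and a short extra analysis. Any session without a usable trace drops out of the adjusted version only and should be counted. The adjusted version may remove part of a true effect, which is why both are shown.
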